#### 2. STUDY OBJECTIVES AND ENDPOINTS

#### 2.1. Primary Objective

 To assess the safety and tolerability of KA34 when administered via intra-articular injection to the knee joint

#### 2.2. Primary Endpoints

• Incidence, relatedness, severity, and duration of treatment emergent adverse events (TEAEs)

#### 2.3. Secondary Objectives

- To identify any dose limiting toxicity and determine the maximum tolerated dose of KA34
- To determine pharmacokinetic properties of KA34 in plasma

#### 2.4. Secondary Endpoints

- Changes from baseline in clinical laboratory test results, vital signs, or electrocardiogram (ECG) results
- Clinically significant findings on physical examination
- Pharmacokinetic parameters of KA34 in plasma including:
  - Maximum observed plasma concentration (Cmax)
  - Dose-adjusted Cmax (Cmax/dose)
  - Time to maximum observed plasma concentration (Tmax)
  - Area under the plasma concentration vs. time curve from time zero to the last quantifiable concentration (AUC $_{0-t}$ )
  - Dose-adjusted AUC0-t (AUC0-t/dose)

- AUC from time zero to infinity (AUC0-∞)
- Dose-adjusted AUC0-∞ (AUC0-∞/dose)
- Terminal elimination rate constant  $(\lambda_z)$
- Terminal half-life (t½)
- Apparent clearance (CL/F)
- Volume of distribution (Vz/F)

#### 2.5. Exploratory Objectives

- To assess changes in cartilage and osteoarthritis symptoms after administration of KA34
- To collect and bank biospecimen samples for exploratory biomarker research

#### 2.6. Exploratory Endpoints

- Serum levels of the N-propertide of type IIA collagen (PIIANP) as a pharmacodynamic marker of collagen synthesis
- Urinary excretion of C-terminal cross-linking telopeptide of type II collagen (CTX-II) as a pharmacodynamic marker of collagen degradation
- Change from baseline in Whole-Organ Magnetic Resonance Imaging Score (WORMS) of the index knee
- Change from baseline of the Western Ontario and McMaster Universities
   Osteoarthritis Index (WOMAC Version 3.1) total score and the WOMAC pain,
   function, and stiffness scores
- Utilize banked biospecimen samples for exploratory research related to drug response in OA

#### 3. STUDY DESIGN

#### 3.1. Study Overview

This is a randomized, double-blind, placebo-controlled study to assess the safety, tolerability, pharmacokinetics, and pharmacodynamics of KA34 when administered via intra-articular injection to subjects with osteoarthritis of the knee. All subjects will receive a 5 mL injection of KA34 or placebo in the affected knee.

The study will consist of approximately 7 cohorts of subjects who will be randomized to receive KA34 or placebo. KA34 will be provided as a solution with a concentration of 200 µg per mL.

KA34 will be administered as a single dose to the following cohorts:

| DOSE            | N PER COHORT               |
|-----------------|----------------------------|
| 50 μg per knee  | 4 (3 – Active & 1 Placebo) |
| 100 μg per knee | 4 (3 – Active & 1 Placebo) |
| 200 μg per knee | 8 (6 – Active & 2 Placebo) |
| 400 μg per knee | 8 (6 – Active & 2 Placebo) |

Once the safety and tolerability of single doses of KA34 have been assessed, multiple-dose administration of KA34 will be evaluated. The multiple-dose portion of the study will be initiated after a thorough review of the safety data from the single-dose cohorts. During the multiple dose portion of the study, KA34 will be administered as 4 weekly doses to the following cohorts:

| DOSE                          | N PER COHORT                |
|-------------------------------|-----------------------------|
| 100 μg per knee per injection | 12 (9 – Active & 3 Placebo) |
| 200 μg per knee per injection | 12 (9 – Active & 3 Placebo) |
| 400 μg per knee per injection | 12 (9 – Active & 3 Placebo) |

The doses administered to subsequent cohorts in either the single or multiple dose portions of the study may be lowered if any safety or tolerability issues are identified which suggest that the planned doses may pose a risk to study participants. Additional dose groups may be added to the study depending on the observed safety and tolerability profile of KA34 or if the pharmacokinetic data permit a higher than anticipated dose while remaining within a safe exposure limit based on the toxicokinetics and safety profile from the nonclinical toxicology studies.

The study will be conducted at approximately 4 sites in the United States. Approximately 60 subjects will be randomized to participate in this trial.

#### 3.2. Dose Escalation

The decision to escalate to the next dose cohort of the study will be made by the sponsor, based on the recommendation of the Data Safety Monitoring Board (DSMB) following a (blinded) review of all available safety information from Day 8 post-dose of the preceding dose cohort in the single dose portion of the study(see Section 9.7, DSMB) The decision to initiate the multiple dose portion of the study will be made by the sponsor, after all cohorts have completed dosing in the single ascending dose portion of the study and based on the recommendation by the DSMB following a (blinded) review of all available safety information from Day 29.

The decision to escalate to the next dose cohort in the multiple dose portion of the study will be made by the sponsor based on the recommendation of the DSMB following a (blinded) review of the available safety data from Day 8 post-dose, after all subjects have been dosed in the preceding dose cohort. The safety information considered during this review will include adverse events, changes in vital sign measurements, clinical laboratory test values, and ECG results. Dose escalation will be stopped if it is determined that the limits of safety or tolerability have been reached; this decision will be made following the recommendation by the DSMB.

The doses administered to subsequent cohorts in either the single or multiple dose portions of the study may be lowered if any safety or tolerability issues are identified which suggest that the planned doses may pose a risk to study participants. Additional dose groups may be added to the study depending on the observed safety and tolerability profile of KA34.

Dose escalation will be paused if any of the following occur:

- 50% or more of the subjects at a given dose level develop similar clinically significant laboratory, ECG, or vital sign abnormalities or severe adverse events (AEs) in the same organ class, indicating dose-limiting intolerance
- A serious adverse event (SAE) that is deemed causally related to KA34 by the DSMB
- Additional safety data from a dose cohort are required to determine whether the limit of safety or tolerability has been reached
- Any other safety findings that, at the discretion of the DSMB, indicate that dose escalation should be halted

If dose escalation is halted, dosing may resume if the DSMB and sponsor determine that there is no unacceptable risk to subjects after a thorough review of the available safety information. The study may be terminated or the protocol may be amended if dosing cannot be resumed without adequate measures to ensure subject safety.

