| VISIT NUMBER   | $1^{\mathrm{I}}$ |                           |      |                   | 2                     |                 |                 |                 |                 | 3                     | 4                            | S                            | 9                            | 7               | 8                      | 6                      | 10                        |
| TIME POST FIRST DOSE                                   | NA               | PRE-
DOSE J | 0    | 15
MIN M       | 30
MIN 1           | 09
MIN       | 06
MIN       | 2
HRS        | 4
HRS        |                       |                              |                              |                              |                 |                        |                        |                           |
| ALLOWABLE VISIT WINDOW                                 | -28 to -1 days   |                           | . 2  | +/-
2
Min N | +/-
3
Min       | +/-
5
Min | +/-
5
Min | +/-
5
Min | +/-
5
Min |                       | +/-
1
Day L | +/-
1
Day L | +/-
1
Day L | +/-
1
Day | +
3
Days         | +/-
7
Days       | +/-
30
Days         |
| Informed Consent                                       | X                |                           | 1    |                   |                       |                 |                 |                 |                 |                       |                              |                              |                              |                 |                        |                        |                           |
| Demography   | X                |                           |      |                   |                       |                 |                 |                 |                 |                       |                              |                              |                              |                 |                        |                        |                           |

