| Vital Signs B                               | X                | X                         |      | X                 | X                     | X               | X               | X               | X               |                       | X                            | X                            | X                            | X               |                        | X                      | X                         |
| 12-Lead ECG  | X                | X                         |      |                   |                       |                 |                 |                 |                 |                       | X                            |                              |                              | X               |                        | ×                      | X                         |
| Tibial-Femoral Radiographs C                | ×                |                           |      |                   |                       |                 |                 |                 |                 |                       |                              |                              |                              |                 |                        |                        |                           |
| Safety Laboratory Tests D                   | ×                | ×                         |      |                   |                       |                 |                 |                 |                 |                       | X                            |                              |                              | ×               |                        | ×                      | X                         |
| Follicle Stimulating Hormone Test E         | X                |                           |      |                   |                       |                 |                 |                 |                 |                       |                              |                              |                              |                 |                        |                        |                           |

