#### 6.3.3. Day 8 (Visit 4)

The following procedures will be completed on Day 8:

- Collect blood and urine samples for safety laboratory tests
- Collect pre-dose blood sample for PK analysis
- Collect pre-dose serum sample for PIIANP assessment
- Collect pre-dose urine sample for CTX-II assessment
- Collect pre-dose serum sample for biospecimen banking (if the subject has consented to provide this optional sample)
- Administer the WOMAC
- Record any changes in concomitant medications

- Conduct targeted physical examination
- Obtain weight
- Obtain pre-dose temperature and seated BP and PR
- Obtain 12-lead ECG
- Collect pre-dose synovial fluid sample for biospecimen banking (if the subject has consented to provide this optional sample)
- Administer KA34 or placebo
- Obtain temperature and seated BP and PR 30 minutes after dosing (+/- 5 minute window)
- Assess adverse events by spontaneous reporting and by asking the subject to respond to a non-leading question such as "How do you feel?"
- Remind the subject about study contraception requirements and confirm highly effective contraception is being used (if applicable)

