# 6.3.4. Day 15 (Visit 5)

The following procedures will be completed on Day 15:

- Collect pre-dose blood sample for PK analysis
- Collect pre-dose serum sample for PIIANP assessment
- Collect pre-dose urine sample for CTX-II assessment
- Collect pre-dose serum sample for biospecimen banking (if the subject has consented to provide this optional sample)
- Record any changes in concomitant medications
- Obtain weight
- Obtain temperature and seated BP and PR
- Collect pre-dose synovial fluid sample for biospecimen banking (if the subject has consented to provide this optional sample)
- Administer KA34 or placebo
- Obtain temperature and seated BP and PR 30 minutes after dosing (+/- 5 minute window)
- Assess adverse events by spontaneous reporting and by asking the subject to respond to a non-leading question such as "How do you feel?"
- Remind the subject about study contraception requirements and confirm highly effective contraception is being used (if applicable)
- Subjects may be discharged after at least 2 hours of safety observation following the last procedure

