### 6.3.5. Day 22 (Visit 6)

The following procedures will be completed on Day 22:

- Collect pre-dose blood sample for PK analysis
- Collect pre-dose serum sample for PIIANP assessment
- Collect pre-dose urine sample for CTX-II assessment
- Collect pre-dose serum sample for biospecimen banking (if the subject has consented to provide this optional sample)
- Record any changes in concomitant medications
- Obtain weight
- Obtain temperature and seated BP and PR
- Collect pre-dose synovial fluid sample for biospecimen banking (if the subject has consented to provide this optional sample)
- Administer KA34 or placebo
- Collect temperature and seated BP and PR 30 minutes after dosing (+/- 5 minute window)
- Assess adverse events by spontaneous reporting and by asking the subject to respond to a non-leading question such as "How do you feel?"
- Remind the subject about study contraception requirements and confirm highly effective contraception is being used (if applicable)
- Subjects may be discharged after at least 2 hours of safety observation following the last procedure

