4. PLANNED ANALYSES

4.1. Data Safety Monitoring Board (DSMB)

The decision to escalate to the next dose cohort (single or multiple dose escalation) of the study will be made by the sponsor, based on the recommendation of the DSMB following a (blinded) review of all available safety information from Day 8 post-dose of the preceding dose cohort. The safety information considered during this review will include adverse events, changes in vital sign measurements, clinical laboratory test values, and ECG results. Reporting for the DSMB is to be handled by the data management team and is outside the scope of this document.

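### Multiple-dose escalation may proceed on Day 8 data, so no lab or ECG after a repeat injection is required before the next dose level

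*Protocol*

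**What the plan says.** **The gate.** Protocol section 3.2 bases escalation in the multiple-dose part on a blinded DSMB "review of the available safety data from Day 8 post-dose, after all subjects have been dosed in the preceding dose cohort". It says the review will cover adverse events, vital signs, laboratory values and ECG results. SAP section 4.1 sets one rule for both parts: it begins "The decision to escalate to the next dose cohort (single or multiple dose escalation" and names Day 8 of the preceding cohort.

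**The clock.** The multiple-dose schedule in the protocol is headed "TIME POST FIRST DOSE". Injections fall on Days 1, 8, 15 and 22.

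**What is collected.**
- Day 8 (section 6.3.3) lists "Collect blood and urine samples for safety laboratory tests" and a 12-lead ECG ahead of the injection. After the injection it lists "Obtain temperature and seated BP and PR 30 minutes after dosing (+/- 5 minute window") and an adverse event assessment.
- Sections 6.3.4 and 6.3.5 ("The following procedures will be completed on Day 15"; "The following procedures will be completed on Day 22") list no safety labs and no ECG. In the schedule, the "Safety Laboratory Tests" and ECG rows are marked at Day 8 and Day 29 and blank at Days 15 and 22.
- Day 29 (section 6.3.6) has safety labs and an ECG, seven days after injection 4.

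**The purpose.** Section 9.1 says cohort sizes were chosen so that safety signals or dose-limiting toxicity can be identified before higher doses are given. Section 2.3 makes the maximum tolerated dose a secondary objective.

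**The concern.** The multiple-dose part exists to learn what repeated weekly injections do. A gate that closes at the second injection can be passed before most of that information is due. For labs and ECG, the required data come seven days after one injection. The single-dose cohorts already supplied that at 100, 200 and 400 µg on their own Day 8 (section 6.2.3). The multiple-dose cohort adds subjects to the same question but does not ask the repeat-dose one.

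The gate from the single-dose to the multiple-dose part does not help. It names Day 29, but the single-dose Day 29 contact has no scheduled labs or ECG and may be a telephone call (section 6.2.4).

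At stake is whether weekly dosing at 200 or 400 µg could start before a cumulative effect at the level below has had a required opportunity to show itself.

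**Working it through.** **Step 1. Cohorts.** 4 + 4 + 8 + 8 + 12 + 12 + 12 = 60, which reproduces the planned total of approximately 60. The multiple-dose part has three levels of 12 subjects (9 KA34, 3 placebo), so there are two planned escalation steps: 100 to 200 µg and 200 to 400 µg.

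**Step 2. Injections received before each scheduled lab and ECG (multiple-dose part).** Count the injections on Days 1, 8, 15 and 22 that precede the assessment, taking Day 8 in the order section 6.3.3 lists it.

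| Lab and ECG visit | Injections before it |
|---|---|
| Day 8 | 1 |
| Day 29 | 4 |
| Day 90 | 4 |
| Day 180 | 4 |

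No scheduled lab or ECG follows exactly two or three injections. The first after any repeat injection is Day 29, which is 29 − 8 = 21 days after the gate.

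**Step 3. What the gate requires from the last subjects enrolled.**

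| Data type | After injection 1 | After injection 2 | After injections 3 and 4 |
|---|---|---|---|
| Labs, ECG | Day 8 | none | none |
| Vital signs | Day 1 and Day 8 | 30 minutes | none |
| Adverse events | Days 1, 2 and 8 | clinic stay only | none |

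The clinic stay means at least 2 hours of observation after the last procedure (schedule footnote K). The next contact after Day 8 is Day 15.

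**Step 4. How much later data might exist anyway.** The documents give no enrolment rate or review lag, so both are assumed. With even enrolment at *r* per week, and the review held *L* days after the last subject's Day 8, subject *i* of 12 has reached Day 29 if

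(12 − *i*) × 7/*r* + *L* ≥ 21.

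Example: *r* = 2 and *L* = 0 gives (12 − *i*) × 3.5 ≥ 21, so *i* ≤ 6 and six subjects qualify.

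| Review lag | 1 per week | 2 per week | 3 per week | 4 per week |
|---|---|---|---|---|
| 0 days | 9 | 6 | 3 | 0 |
| 7 days | 10 | 8 | 6 | 4 |
| 14 days | 11 | 10 | 9 | 8 |

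Entries are subjects of 12 with Day 29 labs and ECG in hand. The amount depends on recruitment speed and review timing, and no rule fixes it.

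**The case against.** **Day 8 post-dose could mean after the last dose.** Day 22 + 7 = Day 29, which would close the gap. Against this, Day 8 is a named visit, the SAP uses one Day 8 rule for both parts, and section 3.2 says subjects have completed dosing where it means that (the step into the multiple-dose part). Neither document states the later reading. If it was intended, a clarifying phrase is all that is needed.

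**Day 8 labs and ECG are not labelled pre-dose.** True; their position rests on list order. But no sample after the injection is required, so the conclusion does not change.

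**Some repeat-injection data are inside the gate.** This stands. A reader might infer that the review sees nothing after a repeat injection. That is wrong: vital signs and adverse events after injection 2 are required on Day 8, and section 3.2 says the review includes both data types. The complete gap is in labs and ECG, together with everything after injections 3 and 4.

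**Later data will often be available.** Also fair. Earlier-enrolled subjects may have reached Day 29, section 9.5 requires ongoing review of safety data, and the DSMB may pause for additional data. The DSMB charter, which is not among the documents, may say more. None of the provisions in the protocol or SAP ties repeat-dose data to the escalation decision.

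**Systemic build-up is unlikely.** Section 1.2.1 reports low plasma levels and rapid clearance in animals, section 1.3.2 reports no remarkable findings at the high dose in the 5-week studies, and SAP section 15.1 expects no quantifiable drug after 4 hours. This lowers the likely yield of the missing labs and ECGs. Those tests also do not measure local knee effects. For the knee, a Day 29 gate mainly adds adverse event and symptom reports after all four injections, since the first post-treatment MRI is on Day 90.

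**Conclusion.** The gap is real and specific. As written, escalation between multiple-dose levels requires labs and ECG after one of four injections. From the last-enrolled subjects it requires only same-visit vital signs and adverse events after the second injection, and nothing after the third or fourth. That does not fully serve the stated aim of section 9.1. It is a worthwhile and cheap correction, not a finding that the trial is unsafe. It rests on reading Day 8 as the visit so named in a schedule timed from the first dose.

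Three stronger readings go beyond the documents.
- A reader might infer that escalation will in fact occur without repeat-dose labs or ECG. The enrolment table shows this only at the fastest assumed rate with no review lag.
- A reader might set the 400 µg dose against the 3-fold factor in section 1.3.2 and call the local margin too small. That factor was used to derive a maximum recommended starting dose and is not a benchmark for the top escalation dose.
- A reader might say the 50% pause criterion in section 3.2 has no denominator. It names the subjects at a given dose level, and section 5 uses dose level for KA34 and placebo recipients together. At most it is ambiguous whether placebo subjects count.

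**What to change.** In protocol section 3.2 and SAP section 4.1, define the gate between multiple-dose levels as DSMB review of safety data through the Day 29 visit of the preceding cohort, seven days after injection 4. If Day 8 post-dose was always meant to follow injection 4, say so in both places.

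**Cost.** No new visits or tests, because Day 29 labs and ECG are already scheduled. The delay is at most about 29 − 8 = 21 days per step, or 2 × 21 = 42 days over the two planned steps. It is smaller where the time overlaps with waiting that would happen anyway. For example, an assumed 7- or 14-day review lag that runs alongside the extra follow-up leaves about 14 or 7 days per step.

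Optionally, add a sentence to section 3.2 saying whether placebo subjects count towards the 50% pause criterion.

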#### 5.7. Maintaining Study Blinding and Breaking the Blind

The Principal Investigator and other site staff not directly involved in the preparation or dispensing of investigational product will be blinded to study treatment throughout the conduct of the study. Blood specimens will be obtained from all subjects for PK analysis to maintain the study blind at the investigator site. Specimens from subjects randomized to placebo will not be routinely analyzed for PK parameters. A blinded monitor will be assigned for each site who will remain blinded until all monitoring for the study has been completed and the database has been released. Personnel of the Sponsor or designated representative involved in the conduct of the study will remain blinded as to study treatment during the conduct of the study. To minimize the potential for bias, treatment randomization information will be kept confidential and will not be released to the blinded investigator or blinded investigator site personnel until the study database has been locked or the investigator requests unblinding for safety reasons.

At the initiation of the study, the site will be instructed on procedures for breaking the blind for safety reasons. The study blind should be maintained whenever possible to avoid bias. The blind may be broken in circumstances when knowledge of the treatment received by a subject is essential for further medical management of the subject. The blind may also be broken if necessary to determine whether dosing or dose escalation should be paused. When the blind is broken, the reason must be fully documented and entered on the case report form (CRF).

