#### 6.3.6. Day 29 (Visit 7)

The following procedures will be completed on Day 29:

- Administer the WOMAC
- Record any changes in concomitant medications
- Conduct targeted physical examination
- Obtain weight
- Obtain temperature and seated BP and PR
- Obtain12-lead ECG
- Collect blood and urine samples for safety laboratory tests
- Collect blood sample for PK analysis
- Collect serum sample for PIIANP assessment
- Collect serum sample for biospecimen banking (if the subject has consented to provide this optional sample)

- Collect urine sample for CTX-II assessment
- Assess adverse events by spontaneous reporting and by asking the subject to respond to a non-leading question such as "How do you feel?"
- Remind the subject about study contraception requirements and confirm highly effective contraception was used for 7 days after the last IP dose (if applicable)

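### Protocol 3.2 is inconsistent on what its safety triggers stop: the only mandatory action is a pause of dose escalation, while its closing paragraph and 5.7 presuppose a hold on dosing that no sentence imposes

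*Protocol*

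**What the plan says.** Protocol 3.2 introduces four triggers with "Dose escalation will be paused if any of the following occur". They are a 50% intolerance rule, an SAE that the DSMB attributes to KA34, a need for more safety data from a cohort, and any other finding at the DSMB's discretion. The first begins "50% or more of the subjects at a given dose level develop similar clinically significant laboratory, ECG, or vital sign abnormalities" and also covers severe adverse events in one organ class.

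The section fixes the meaning of escalation: "The decision to escalate to the next dose cohort in the multiple dose portion of the study will be made by the sponsor", on the DSMB's recommendation. Its separate stop sentence also concerns escalation, and its dose-lowering sentence concerns later cohorts.

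Two other places speak of dosing itself:

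- Protocol 3.2, closing paragraph: "If dose escalation is halted, dosing may resume if the DSMB and sponsor determine that there is no unacceptable risk to subjects". The next sentence allows termination or amendment if dosing cannot be resumed.
- Protocol 5.7: "The blind may also be broken if necessary to determine whether dosing or dose escalation should be paused".

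In the multiple-dose part, injections fall on Days 1, 8, 15 and 22. SAP 4.1 repeats the Day 8 escalation review and adds no rule on holding doses.

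**The concern.** In a single-dose cohort, pausing escalation is close to pausing exposure, because each subject already dosed has nothing further to receive. In a four-injection regimen the two differ. A cohort can meet a trigger with most of its injections still to come, and the one action that 3.2 states applies to the next cohort and not to the one that produced the signal.

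The scope is unclear in three places: the triggering cohort's remaining injections, subjects newly enrolled into that cohort, and a higher-dose cohort already being dosed. The third can arise because escalation may follow Day 8 data, while the lower-dose cohort still has injections on Days 15 and 22.

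The last planned cohort (400 µg × 4) shows the problem most clearly. No planned cohort follows it, so an escalation pause alone stops no planned injection. It could only block the optional extension in Protocol 3.1: "Additional dose groups may be added to the study depending on the observed safety and tolerability profile of KA34".

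At stake is whether, in a first-in-human trial, meeting a pre-specified trigger stops further exposure by itself or only through a separate discretionary decision.

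**Working it through.** **Step 1. The wording side by side.**

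| Place | What it acts on | Force |
|---|---|---|
| 3.2, trigger list | Dose escalation | Mandatory |
| 3.2, stop sentence | Dose escalation | Mandatory once limits are judged to be reached |
| 3.2, dose lowering | Later cohorts | Permissive |
| 3.2, closing paragraph | Resumption of dosing | Permissive; presupposes a hold |
| 5.7 | Dosing or escalation, named separately | Permissive unblinding to decide |
| 9.7 | The study | DSMB recommendation |
| 6.4 and 14 | The subject; the study | Discretionary |

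Neither 3.2, 5.4, 6.3.3 to 6.3.5, 9.7 and 14 of the protocol nor SAP 4.1 contains a sentence that withholds remaining injections when a trigger is met.

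**Step 2. Check of the cohort sizes.** The design tables give 4 + 4 + 8 + 8 + 12 + 12 + 12 = 60, which matches the stated total of about 60. Each multiple-dose cohort has 12 subjects, 9 on KA34 and 3 on placebo.

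**Step 3. The 50% trigger.** Taking the 12 subjects of one multiple-dose cohort as the denominator, 0.5 × 12 = 6 subjects.

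**Step 4. Injections outstanding.** If all subjects are dosed in step, the remaining injections are 12 × (4 − doses given), and those of KA34 are 9 × (4 − doses given).

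| Trigger recognised after | All injections left | KA34 injections left | Left per KA34 subject at 400 µg |
|---|---|---|---|
| Day 1 injection | 12 × 3 = 36 | 9 × 3 = 27 | 3 × 400 = 1,200 µg |
| Day 8 injection | 12 × 2 = 24 | 9 × 2 = 18 | 2 × 400 = 800 µg |
| Day 15 injection | 12 × 1 = 12 | 9 × 1 = 9 | 400 µg |
| Day 22 injection | 0 | 0 | 0 |

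The full planned dose at 400 µg is 4 × 400 = 1,600 µg per KA34 subject. The Day 1 row could apply only to adverse events or vital signs, since the first post-dose laboratory tests and ECG are on Day 8. The Day 8 row assumes that those results arrive after that day's injection.

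**Step 5. Scheduled laboratory tests and ECGs.** Section 6.3.3 (Day 8) includes "Collect blood and urine samples for safety laboratory tests" and an ECG. Sections 6.3.4 and 6.3.5 (Days 15 and 22) schedule neither. Both return in 6.3.6, under "The following procedures will be completed on Day 29". The interval is 29 − 8 = 21 days and spans the Day 8, 15 and 22 injections. Vital signs and adverse events are still collected on Days 15 and 22.

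**The case against.** The strongest reply is that the closing paragraph belongs to the rule. Resumption of dosing can be made conditional only if dosing has stopped, so a hold is implied, and 5.7 points the same way. This stands in part. It rules out a reading that a reader might infer from the trigger list alone, that the protocol directs the weekly injections to continue after a trigger. The documents do not say that. They imply a hold without imposing it or setting its scope.

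A reader might also infer that nothing else protects these subjects. That is not supported either:

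- Under 9.7 the DSMB may recommend a hold after an intervention-related SAE. Without that condition, it also advises on continuing, modifying or stopping the trial, a remit wide enough for a 50% intolerance signal.
- Section 9.5 provides for ongoing review of safety data. Section 7.1.1 allows unscheduled laboratory tests, and the Schedule of Activities allows unplanned visits. The 21 days are therefore a gap in scheduled laboratory tests and ECGs, not in monitoring.
- Subjects may be withdrawn for safety (6.4), urgent safety measures may be taken (12.4), and the study may be terminated (14).

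The 50% trigger itself needs judgement on similarity and clinical significance. The scenario also requires six affected subjects and decision-makers who leave dosing running. These points limit the practical risk. They do not supply the missing instruction: every route is discretionary, and none makes a hold follow from meeting the 50% trigger. The DSMB charter may contain such a rule but is not among the documents. Even so, it would leave the inconsistency in the protocol that sites follow.

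**Conclusion.** The concern holds as an internal inconsistency in Protocol 3.2, and it should be fixed. The mandatory action covers escalation only, while the closing paragraph and 5.7 presuppose a dosing hold that is never imposed. The practical gap is mainly the 50% trigger. The SAE and discretionary triggers already depend on a DSMB judgement, and the DSMB can recommend a hold at the same time.

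The exposure whose status is unclear after a Day 8 laboratory or ECG signal is up to 24 injections per multiple-dose cohort (18 of KA34), or half the planned dose per KA34 subject (800 of 1,600 µg at 400 µg). It falls to 12 injections (9 of KA34) if the trigger is recognised only after the Day 15 injection. These counts illustrate the scope and do not predict what would happen. They assume that all 12 subjects are dosed in step. The documents give no enrolment pace, and staggered dosing could move the counts in either direction.

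**What to change.** Amend Protocol 3.2 as follows.

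1. For the 50% intolerance trigger and the KA34-related SAE trigger: *dose escalation and all further dosing (remaining injections and newly enrolled subjects) in the affected cohort and in any ongoing cohort at the same or a higher dose will be paused pending DSMB review, including in the final planned cohort.*
2. Keep the trigger for additional safety data as an escalation pause.
3. Let the discretionary trigger cover dosing or dose escalation.
4. Begin the closing paragraph: *If dosing or dose escalation is paused, it may resume if…*
5. State that an injection pushed beyond its ±1 day window by a pause is given or omitted as the DSMB and sponsor decide, keeping the 7-day minimum between injections (Schedule of Activities, multiple-dose footnote L).

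The cost is a few sentences and a check that the DSMB charter agrees. Section 5.7 can stay as it is. The downside is a possible delayed or missed weekly injection if a trigger is met, which item 5 covers.
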